- 5. Medical history (name of disease or syndrome (diagnosis], classification of history or concurrent disease..)
 - * History: Chronic disease (including allergy), disease requiring treatment, disease or disorder with surgery, hospitalization or sequelae, and other relevant disease or syndrome that are cured before commencement of XELJANZ treatment (no treatment and no symptoms)
 - * Concurrent disease: Chronic disease (including allergy), disease requiring treatment disease or disorder with surgery, hospitalization or sequelae, and other relevant disease or syndrome that require any treatment or require no treatment but have residual symptoms at the time of commencement of XELJANZ treatment

6. Prior treatment for ulcerative colitis

The status of prior treatment (drug and non-drug therapy) for the last episode before commencement of XELJANZ treatment (an episode treated with XELJANZ) should be recorded.

For biological products, the status of use throughout the past treatment of ulcerative colitis should be recorded, and if any biological product was used, the name of the product and the classification of primary failure or secondary failure• should be recorded.

*: Primary failure: Lack of effectiveness or insufficient effectiveness with treatment for an appropriate period at the approved dosage and administration

Secondary failure: Loss of effectiveness (relapse) with continued treatment after achieving a clinical response (remission) with treatment for an appropriate period at the approved dosage and administration

Indeterminate: Treatment is discontinued due to any reason other than "not effective" (e.g., adverse events) and determination whether it is primary failure or secondary failure cannot be made

- 7. Smoking history (status of smoking at the start of the investigation)
- 8. Family history of malignant tumor (including lymphoma)

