| Version/ | Summary of Changes/Comments |
|-------------|--|
| Date/ | |
| Author(s) | |
| | 8.2.3.3. Subgroup analyses |
| | • Made editorial revisions regarding the content of "Analyses by dosage subgroup". |
| | 9. LISTINGS |
| | • Added "AEs considered as out of collection-period" as a listing item. |
| | Made other typographical corrections. |
| 4.0 | 6.1. Safety Endpoints |
| 30-MAY-2022 | • Added descriptions that events that should be handled as an element of the safety |
| PPD | specification should follow the definitions presented in the Appendix of Tofacitinib |
| | Periodic Safety Update Report (PSUR), and that the definition of an event that is not |
| | defined in the PSUR is presented in this SAP. |
| | 7. HANDLING OF MISSING DATA |
| | • Added a description how to impute the date of the end of treatment when it is missing. |
| | • Added a description how to impute the end date for concomitant therapies (drug and |
| | non-drug) when it is missing. |
| | 8.2.2. Patient characteristics and medical history |
| | • Described what kinds of past history and complication will be considered. |
| | • Described what kinds of concomitant drug, non-drug therapy, and prior treatment will |
| | be considered. |

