7. HANDLING OF MISSING DATA

If the date of the end of the treatment with this drug is missing, the date of the last observation recorded in the CRF entry "Status of the treatment with Xeljanz" will be used instead. Treatment completers whose end-of-treatment date has not been recorded will be handled in a way that the treatment continued until the last observation date.

Similarly, if the date of the end of a drug therapy or non-drug therapy is missing, the date of the last observation will be used instead.

If the severity, action taken, or outcome for an AE is missing, it will be treated as "unknown" when summarizing data.

If an efficacy endpoint was not measured within its visit window (Appendix 1), it will be treated as missing data and no imputation will be done. The partial Mayo score will be treated as missing data unless the stool frequency subscore, rectal bleeding subscore, and physician's global assessment subscore have all been measured. Similarly, the Mayo score will be treated as missing data unless the stool frequency subscore, rectal bleeding subscore, findings of flexible sigmoidoscopy subscore, and physician's global assessment subscore have all been measured.

Cleaning-uncompleted data will be in principle handled as follows:

- Items for which data are missing: For both purposes of summarization and listing, the corresponding data will be treated as missing data (or as "unknown" if they are a categorical variable).
- Items for which data are inconsistent: For both purposes of summarization and listing, the inconsistent data will be treated as missing data. A list of how each set of inconsistent data have been handled will be presented separately.
- No signature: For both purposes of summarization and listing, any record in a CRF with no signature of a contract physician (including when the CRF is signed only by individuals other than contract physicians) will be treated as missing data.

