Using the SAS and EAS, a breakdown of patients by each of the following factors will be presented in terms of n and proportion. Concomitant medications and non-drug therapies will be defined in align with the data collection period for adverse reactions and AEs so that relationship to adverse reactions and AEs can be assessed.

- Concomitant medications (drugs recorded in the CRF entry "Drug therapies for UC prior treatment and concomitant therapies" that were used in the period from the start of the treatment with this drug to the discontinuation of treatment or 60 weeks after the start of treatment, whichever came first)
- Non-drug therapies (non-drug therapies recorded in the CRF entry "Non-drug therapies for UC prior treatment and concomitant therapies" that were used in the period from the start of the treatment with this drug to the discontinuation of treatment or 60 weeks after the start of treatment, whichever came first)
- Prior medications (medications recorded in the CRF entry "Past history of treatment for UC biological therapeutics", and medications recorded in the CRF entry "Drug therapies for UC prior treatment and concomitant therapies" of which administration had been started by the day before the start of the treatment with this drug)

• Dosing status of Xeljanz tablets

Using the SAS (including the subgroups by mean daily dose) and the set of patients treated for a long term (including the subgroups by mean daily dose), dosing data for this drug will be summarized with respect to the following aspects:

- Starting daily dose [5 mg, 10 mg, 15 mg, 20 mg, >20 mg]
- Duration of treatment [\leq 15 weeks, >15 to \leq 30 weeks, >30 to \leq 45 weeks, >45 to \leq 60 weeks, >60 to \leq 75 weeks, >75 to \leq 90 weeks, >90 to \leq 105 weeks, >105 to \leq 120 weeks, >120 to \leq 135 weeks, >135 weeks]
- Total duration of treatment (patient-years) [≤15 weeks, >15 to ≤30 weeks, >30 to ≤45 weeks, >45 to ≤60 weeks, >60 to ≤75 weeks, >75 to ≤90 weeks, >90 to ≤105 weeks, >105 to ≤120 weeks, >120 to ≤135 weeks, >135 weeks] (The total duration of treatment in each category and the accumulated total duration of treatment will be presented.)
- Mean daily dose by duration of treatment (mg) (summary statistics) [<15 mg, ≥15 mg] [<17 mg,
 ≥17 mg], with the following categories for the duration of treatment:
 - Any duration of treatment
 - Duration of treatment ≤15 weeks
 - Duration of treatment > 15 to ≤ 30 weeks
 - Duration of treatment >30 to <45 weeks

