- Malignancy
- Cardiovascular events (including lipids increased and hyperlipidaemia)
- Cardiovascular events (excluding lipids increased and hyperlipidaemia)
- Lipids increased and hyperlipidaemia
- Rhabdomyolysis and myopathy

In addition, patients who experienced adverse reactions in the scope of the safety specification will be summarized in terms of n and proportion by SOC and PT, for different kinds of action taken and outcome.

Timing of onset of elements in the safety specification

Patients who experienced adverse reactions of each element in the safety specification will be summarized by timing of first onset, in terms of n and proportion as well as incidence and its 95% CI. For the purpose of summarization by time to onset, the denominator to calculate the proportion will be the number of patients who took at least one dose during each time category, and the denominator to calculate the incidence will be the duration of exposure in each time category. The categories for onset timing will be given by $[\le 15 \text{ weeks}, > 15 \text{ to} \le 30 \text{ weeks}, > 30 \text{ to} \le 45 \text{ weeks}, > 45 \text{ to} \le 60 \text{ weeks}]$, except for malignancy, for which given by ≤ 15 weeks, ≥ 15 to ≤ 30 weeks, ≥ 30 to ≤ 45 weeks, ≥ 45 to ≤ 60 weeks, ≥ 60 to ≤ 75 weeks, >75 to ≤ 90 weeks, >90 to ≤ 105 weeks, >105 to ≤ 120 weeks, >120 to ≤ 135 weeks, >135 weeks].

Relationship between concomitant drugs and adverse reactions

To investigate the relationship between concomitant biologics/immunosuppressants or concomitant CYP3A4 inhibitors/CYP2C19 inhibitors and adverse reactions included in the scope of the safety specification, development of those adverse reactions will be summarized in patients with and without concomitant use of a biologic/immunosuppressant and in patients with and without concomitant use of a CYP3A4 inhibitor/CYP2C19 inhibitor, by PT in terms of number of patients. Concomitant drugs used after the first onset of a target event will be excluded from the summarization. Concomitant drugs considered in this investigation include:

- Biologics (including recombinants)/immunosuppressants: abatacept, adalimumab, anakinra, azathioprine, baminercept, canakinumab, certolizumab, certolizumab pegol, cyclosporine, efalizumab, etanercept, golimumab, infliximab, ofatumumab, rituximab, Syk kinase inhibitors, tacrolimus hydrate, tocilizumab, sarilumab, zanolimumab, vedolizumab, ustekinumab, secukinumab, ixekizumab, and 6-mercaptopurine

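### The SAP's missing-end-date rule can turn a UC therapy stopped before Day 1 into a concomitant therapy when it sits in a CRF entry that pools prior and concomitant treatment

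*SAP*

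**What the plan says.** SAP section 7 fills a missing stop date for other UC treatment in one sentence: "if the date of the end of a drug therapy or non-drug therapy is missing, the date of the last observation will be used" as the substitute. It covers drug and non-drug therapy and attaches no condition on when the therapy began or whether it was known to be continuing.

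SAP 8.2.2 then defines concomitant drugs as those in the CRF entry for UC drug therapies "that were used in the period from the start of the treatment with this drug to the discontinuation of treatment or 60 weeks" from the start of treatment, whichever is earlier. By its name, that entry covers both prior treatment and concomitant therapy. The definition for non-drug therapies is built the same way. Prior medications are defined by start date (before Day 1), with a second source in a separate CRF entry for past biologic treatment.

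Pre-treatment records are expected in the data. Protocol 7.3.2 asks for "The status of prior treatment (drug and non-drug therapy) for the last episode before commencement of XELJANZ treatment". Protocol 7.3.4, in contrast, confines concomitant therapy to treatment given from the start of XELJANZ onward.

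SAP 8.2.3.1 uses the classification to tabulate safety-specification reactions "in patients with and without concomitant use of a biologic/immunosuppressant", and likewise for CYP3A4/CYP2C19 inhibitors. SAP 8.2.3.2 repeats this for adverse events.

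**The concern.** In a pooled entry, the stop date is what separates a drug that ended before Day 1 from one that ran on into XELJANZ treatment. When that date is missing, the rule always assumes the drug ran on. A patient whose tacrolimus or azathioprine ended before Day 1, with no stop date in the chart, is then shown as taking it alongside XELJANZ until the last observation.

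Two outputs are at stake. The 8.2.2 breakdowns of concomitant drugs and non-drug therapies, in both the safety and effectiveness sets, may overstate combined use. The tables in 8.2.3.1 and 8.2.3.2, which look at safety-specification events under combined immunosuppression, may place patients who had no combined exposure in the group with concomitant use. If true combined use is uncommon, a few such patients could form a noticeable part of that group.

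**Working it through.** The plan states no figure to reproduce, so the check applies its rules to example records. It assumes that use in the window is judged from recorded or imputed start and stop dates.

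**Step 1: example records.** Take a last observation on Day 420 (60 × 7, assumed), with XELJANZ continuing to that day. A therapy is prior if it started before Day 1. It is concomitant if it started by Day 420 and its recorded or imputed stop is Day 1 or later.

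| Start | Recorded stop | Stop used | Prior | Concomitant |
|---|---|---|---|---|
| Day −120 | Day −30 | Day −30 | yes | no |
| Day −120 | missing | Day 420 | yes | yes |
| Day −120 | Day 200 | Day 200 | yes | yes |

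The second record gets the same classification as the third, whether the drug really stopped before Day 1 or not. Being prior does not stop it from being concomitant, because prior status depends on the start date alone.

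**Step 2: later filters.** The tables in 8.2.3.1 and 8.2.3.2 leave out drugs used after the first onset of the event. A falsely extended drug began before Day 1, so it counts as used before any onset and stays in.

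**Step 3: which therapies reach which output.**
- Azathioprine, 6-mercaptopurine, tacrolimus and cyclosporine are on the biologic/immunosuppressant list, so a record in the pooled entry can reach both the 8.2.2 breakdown and the tables. Tacrolimus and cyclosporine are also on the CYP inhibitor list, so one record can move a patient in both comparisons.
- A listed biologic is affected only if it is recorded in the pooled entry. The past-history entry for biologics feeds prior medications only.
- Steroids and blood cell component removal are on neither list. They can change only the 8.2.2 breakdowns.

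**Step 4: how many patients.** The documents do not say. As illustration only, with the planned 470 in the safety set:

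misclassified patients = 470 × (share with a prior-only therapy in the pooled entry) × (share of those with no stop date)

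- 20% and 2%: 470 × 0.20 × 0.02 = 1.9
- 40% and 5%: 470 × 0.40 × 0.05 = 9.4
- 60% and 20%: 470 × 0.60 × 0.20 = 56.4

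All these shares are assumptions. The width of the range, about 2 to 56, shows that the documents do not fix the size. For the tables in 8.2.3.1 and 8.2.3.2, only therapies on the two lists would count.

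**Step 5: comparison within SAP section 7.** For time to onset, an unknown end of observation in an event-free patient is set to the last date on which XELJANZ administration can be confirmed. The rule for other UC therapies asks for no such confirmation.

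**The case against.** The strongest objection is that the CRF is not in the documents. It may carry an ongoing box or a prior/concomitant field, or a blank stop date may be the way continuing treatment is recorded. In that last case the SAP rule is right, and treating such records as prior only would misclassify drugs that did continue. This stands, and it shapes the fix.

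Second, the SAP 4.0 revision history says "Added a description how to impute the end date for concomitant therapies (drug and" non-drug), which suggests a narrower intention than the section 7 sentence. It is fair evidence of intent and the difference is not an error in itself, but it does not settle the matter. For a drug started before Day 1, whether it is concomitant depends on the date that is missing.

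Third, a reader might infer that every earlier UC therapy is affected, with a past anti-TNF agent as the obvious case. The documents do not support this, because biologics recorded only in the past-history entry cannot become concomitant by this route.

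Fourth, a reader might infer that a risk ratio for combined use will be pulled toward 1 by a calculable amount. The 8.2.3.1 and 8.2.3.2 tables give numbers of patients by preferred term, not risk ratios. The ratios in 8.2.3.3 concern dose level and the patient factors of 8.2.2, which include no concomitant-drug factor, and patient-factor ratios are withheld where fewer than 10 patients had events. The Appendix 2 mock-up has a generic row for a co-administered drug, but it is only an example layout.

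Finally, sponsor queries under protocol 7.6.5 may recover many missing dates. That would reduce the number of affected records without saying how the remainder should be classified.

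**Conclusion.** The point holds in a limited form. As written, SAP sections 7 and 8.2.2 together count a therapy in the pooled entries as concomitant when it started and stopped before Day 1 and its stop date was not recorded. That is at odds with the protocol's notion of concomitant therapy, and no later step removes it. The affected outputs are the 8.2.2 concomitant breakdowns and, for listed drugs, the count tables in 8.2.3.1 and 8.2.3.2.

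The effect may be negligible or material; the documents do not allow a choice between the two. A reader might take it as a threat to the main results, but it is not one: the primary adverse-reaction incidence and partial Mayo remission do not use the stop dates of other UC therapies. The conclusion assumes that classification follows the dates and that the CRF does not already mark continuation in a way the analysis uses.

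**What to change.** In SAP section 7, state that the last-observation date replaces a missing stop date only for therapies that started on or after Day 1, or that the CRF shows to be in use on or after Day 1 through an ongoing flag, a prior/concomitant field or another record. List therapies that started before Day 1 with no stop date and no such evidence as concomitant use unknown. Present the 8.2.2 breakdowns and the 8.2.3.1 and 8.2.3.2 tables by concomitant use twice, with and without these records counted as concomitant.

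If a blank stop date is the CRF's way of recording continuation, say so in section 7, keep the present rule as the main analysis, and use the version without the ambiguous records as the check.

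The cost is a short change to section 7, one listing and one repeat set of tables, with no new data collection. The drawback is that some drugs that did continue may be held as unknown; the paired tables show how much that matters.

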7.2.5. Observation period

The duration of observation will be 60 weeks (14 months) from the date of treatment commencement (Day 1). However, patients who are treated with XELJANZ for more than 60 weeks after the date of treatment commencement will be continuously followed up until the end of the investigation period * (June 2021). For patients who discontinue XELJANZ, information until the discontinuation will be collected.

*: Date of the last observation before June 2021

This study will be conducted using booklet type CRF. Investigator will complete each booklet of CRFs for each observation period in Table 1. However, for patients who discontinue XELJANZ, information until the discontinuation will be collected.

Name of CRF	Observation period
Booklet 1	Treatment commencement to Week 26 (Month 6) of treatment
Booklet 2	Week 27 (Month 7) to Week 60 (Month 14) of treatment
Booklet 3	Week 61 (Month 15) to end of the investigation period (June 2021)

Table 1. Name of CRF and observation period

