7.3.8. Clinical evaluation on effectiveness

The record of the clinical evaluation on effectiveness against ulcerative colitis from baseline (including the date of treatment commencement) to the date of completion of the observation period (or date of XELJANZ discontinuation) should include the results of evaluations based on the following rating scales.

1. Stool frequency:

0 point = Normal number of stools for the patient

1 point = 1-2 stools more than normal

2 points = 3-4 stools more than normal

- 3 points = 5 or more stools more than normal
- 2. Rectal bleeding:
 - 0 point = No blood seen
 - 1 point = Slight of blood with stool less than half the time
 - 2 points =Obvious blood with stool most of the time
 - 3 points = Blood alone passed
- 3. Findings of flexible sigmoidoscopy:
 - 0 point = Normal or inactive disease
 - 1 point = Mild disease (erythema, decreased vascular pattern, mild fragility)
 - 2 points = Moderate disease (marked erythema, absent vascular pattern, any friability, erosion)
 - 3 points = Severe disease (spontaneous bleeding, ulceration)
- 4. Physician's global assessment:
 - 0 point = Normal
 - 1 point = Mild disease
 - 2 points = Moderate disease
 - 3 points = Severe disease

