7.7.2.2. Analysis for effectiveness evaluation

In the effectiveness analysis set, the rate of remission based on partial Mayo score will be set as primary analysis items.

Detailed methodology for summary and statistical analyses of data collected in this study will be documented in a Statistical Analysis Plan (SAP), which will be dated, filed and maintained by the sponsor. The SAP may modify the plans outlined in the protocol; any major modifications of primary endpoint definitions or their analyses would be reflected in a protocol amendment.

- 7.8. OTHER NECESSARY MATTERS Not applicable.
- 8. ORGANIZATIONAL SYSTEM FOR STUDY IMPLEMENTATION

Regarding the organizational system in this study, refer to the appendix I of "the risk management plan".

9. NAME, ADDRESS AND OUTSOURCED OPERATIONS OF THE PERSON WHO WAS CONTRACTED WITH THE OPERATIONS

Name: PPD

Address: PPD

Scope of the outsourced operations: Drafting of study protocol and management of operation study, etc. Name: PPD

Address: PU

Scope of the outsourced operations: Establishment, operation and maintenance of the EDC system.

Name: PPD

Address: PPD

Scope of the outsourced operations: Contract-related operations, reception of registration forms, delivery/reception of CRFs, data management, medical writing etc.

Name: PPD

Address: PPD

Scope of the outsourced operations: Establishment of the EDC system, data management, tabulation analysis

10. ADDITIONAL MEASURES THAT MAY BE IMPLEMENTED BASED ON THE STUDY RESULTS AND CRITERIA FOR DETERMINATION OF THE INITIATION

Review the risk management plan including the following contents at the scheduled timing of milestones.

I. Review the necessity for changing the contents of risk minimization activities for the current safety specifications.

- 2. Review the necessity for changing the contents of this study plan including the presence or absence of new safety specifications (continuation of the study, implementation of additional study, etc.).
- 3. Review the necessity for formulating risk minimization measures for new safety specifications.

11. SCHEDULED TIMING OF MILESTONES AND THEIR RATIONALES FOR REPORTING OF STUDY IMPLEMENTATION STATUS AND EVALUATION OF OBTAINED RESULTS TO THE PMDA

Review and report the safety and effectiveness at the time of reporting the Periodic Safety Reports and completion of the study.

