2.1. Study Design

This is a multicenter cohort investigation to be conducted in patients with ulcerative colitis treated with XELJANZ in clinical settings.

• Registration criteria

Patients must meet all of the following inclusion criteria to be eligible for inclusion in the study:

- •Patients with ulcerative colitis treated with XELJANZ
- •Patients naive to XELJANZ in the treatment of ulcerative colitis
- Sample size

470 to be collected in the safety analysis set (495 to be registered*)

• Rationale

Based on the results of clinical studies conducted up to approval, the incidence of herpes zoster in Japanese patients with ulcerative colitis chronically treated with XELJANZ was higher than that in the overall population of the studies. Therefore, on the assumption that the true incidence of herpes zoster in Japanese patients with ulcerative colitis is 8/100 person-years, the sample size will be 470 when the probability of the lower limit of 95% confidence interval for the incidence of herpes zoster not falling below 4/100 person-years (results for the overall population of the studies) is 80%.

- *: If it is assumed that 5% of the registered patients are unevaluable for the safety due to failure to show up or other reasons, 495 patients need to be registered to ensure that 470 patients are included in the safety analysis set.
- Safety specification

Important Identified Risks

- Serious infections (including tuberculosis, pneumonia, pneumocystis pneumonia, sepsis, opportunistic infection)
 - Herpes zoster
 - Neutropenia, lymphopenia, oligochromemia
 - Hepatic impairment
 - Reactivation of hepatitis B virus
 - Gastrointestinal perforation
 - Interstitial lung disease
 - Venous thrombosis
 - Malignant tumor
 - Cardiovascular event

Important Potential Risks

• Rhabdomyolysis, myopathy

Important Missing Information

Not applicable.

• Observation period

Each patient will be observed for 60 weeks from the start day of the treatment with this drug. Patients treated with this drug for more than 60 weeks will, however, be observed to the end of this study (June 2021). For patients who discontinued the treatment with this drug, data will be collected until the discontinuation.

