8.2.4. Effectiveness analyses

In this study, the proportion of patients who achieved the remission based on the partial Mayo score will be the primary effectiveness endpoint.

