8.2.4.1. Effectiveness assessment based on the partial Mayo score

• Proportions of patients who achieved study endpoints based on the partial Mayo score

The proportion of patients who achieved each study endpoint based on the partial Mayo score (remission or clinical response) will be calculated with its 95% CI for each study visit. The definition of the study visits should follow "10.1. Appendix 1: Details of Data Handling".

The definition of the endpoints based on the partial Mayo score is shown in Table 1.

Table 1. Endpoints Based on the Partial Mayo Score

| Endpoint | Definition |
|----------------------|---|
| Remission based on | The patient is called to have achieved remission if they meet all the following criteria: |
| the partial Mayo | ● Partial Mayo score ≤2 |
| score | • Stool frequency subscore ≤1 |
| | • Rectal bleeding subscore ≤1 |
| | • Physician's global assessment subscore ≤1 |
| Clinical response | • The decrease from baseline in the partial Mayo score ≥2 |
| based on the partial | |
| Mayo score | |

• Changes in the partial Mayo score

Summary statistics will be presented for each study visit regarding the partial Mayo score and the change from baseline in the partial Mayo score. For the change from baseline, its 95% CI will also be presented. The definition of the study visits should follow "10.1. Appendix 1: Details of Data Handling".

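### The primary remission rate has no named visit and no stated per-visit denominator; if it is read among assessed patients, the later fixed-visit rates probably overstate remission in the effectiveness analysis set

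*SAP*

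**What the plan says.** - **Endpoint and population.** Protocol 7.7.2.2: "In the effectiveness analysis set, the rate of remission based on partial Mayo score will be set as primary analysis items". SAP 8.2.4 repeats it: "the proportion of patients who achieved the remission based on the partial Mayo score will be the primary effectiveness endpoint". Neither names a time point.
- **Timing.** SAP 8.2.4.1 says that the proportion "will be calculated with its 95% CI for each study visit". Appendix A1.1 lists ten post-baseline visits (Weeks 2 to 60) plus End of treatment, which is the last dose plus or minus two weeks. No denominator is given for any of them.
- **Missing scores.** SAP 7, on an effectiveness measure not taken in its window: "it will be treated as missing data and no imputation will be done". The partial Mayo score also counts as missing unless all three subscores are present.
- **Stopping.** Protocol 7.2.5: "For patients who discontinue XELJANZ, information until the discontinuation will be collected". SAP 2.1 agrees: "For patients who discontinued the treatment with this drug, data will be collected until the discontinuation". Protocol 7.3.8 collects the scores "from baseline (including the date of treatment commencement) to the date of completion of the observation period (or date of XELJANZ discontinuation").
- **Reasons for stopping.** Protocol 7.3.10 records insufficient effectiveness, adverse event, death, remission, failure to attend and other.
- **EAS membership.** SAP 5.2 excludes only patients with no effectiveness assessment at all or with the wrong disease. A single subscore or one faecal calprotectin value is enough to be in the set.

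**The concern.** Being in the EAS does not mean having a partial Mayo score at a given visit, so naming the EAS does not settle the denominator. If a missing score is simply missing, the divisor at each visit is the patients scored in that window.

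Take a patient who stops at Week 10 for lack of effect. That patient may be scored in the Week 8 window, but from Week 16 onward is normally in neither numerator nor denominator. The rate can then rise with no patient improving. If 40 of 100 patients are in remission throughout and 30 non-remitters leave, it moves from 40/100 = 40% to 40/70 = 57%.

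Remission among patients still assessed is a legitimate description of chronic use, but it is not the share of EAS patients in remission, and a reader of the report may take it for that. With no visit named, any of eleven rates could also be called the primary result.

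Elsewhere the SAP is more exact. For safety by time period it defines the denominators (8.2.3.1 to 8.2.3.3), and for effectiveness subgroups it names the visit (8.2.4.5).

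**Working it through.** **No figure to reproduce.** The documents state no expected remission rate, discontinuation rate or effectiveness precision. Every number below is an assumption chosen to show the mechanism.

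**Formula.** Let s be the share of the EAS that stopped before the visit, p remission among those assessed, and m remission among stoppers, with all continuers assessed.
- Rate among assessed patients: p
- Rate over all EAS patients: p(1−s) + m·s
- Difference: p − [p(1−s) + m·s] = s(p−m)

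The difference is positive when m < p, zero when m = p and negative when m > p.

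**Range.** For s = 20–60%, p = 50–80% and m = 0–30%, the overstatement runs from 0.2 × (0.5 − 0.3) = 4 points to 0.6 × (0.8 − 0) = 48 points. With p = 70% and m = 80% it reverses: 0.2 × (0.7 − 0.8) = −2 points at s = 20%, and −6 points at s = 60%.

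**Worked example.** Take 400 EAS patients able to reach the visit. Of these, 120 stopped earlier (60 lack of effect, 40 adverse event or other, 20 remission), and 280 continued and were all scored, 168 of them in remission.

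| Rate | Calculation | Result (exact 95% CI) |
|---|---|---|
| Assessed patients only | 168/280 | 60.0% (54.0–65.8) |
| Lack-of-effect stops as non-remitters, remission stops as remitters, other stops missing | (168+20)/(400−40) = 188/360 | 52.2% (46.9–57.5) |
| Same, other stops as non-remitters | 188/400 | 47.0% (42.0–52.0) |
| All 120 stoppers as non-remitters | 168/400 | 42.0% (37.1–47.0) |

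Check of the third row: s = 120/400 = 0.30 and m = 20/120 = 0.167, so s(p−m) = 0.30 × (0.60 − 0.167) = 13 points, and 60 − 13 = 47%.

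**Unscored continuers.** Suppose 56 of the 280 continuers also lack a score, leaving 134/224 = 59.8% observed.
- If all 20 remission stoppers were last scored in remission, the sensitivity result runs from (134+20)/400 = 154/400 = 38.5% to 154/(400−40−56) = 154/304 = 50.7%.
- If none of them has a usable score, they join the unresolved group, and the range is 134/400 = 33.5% to 134/(400−40−56−20) = 134/284 = 47.2%.

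The handling of remission stoppers therefore matters and must be written down.

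**What the planned outputs already show.** The number scored appears at each visit (SAP 8.1.1 with 8.2.4.1), remitters are counted (8.1.3) and the EAS size is reported (8.2.1). A reader can therefore form remitters divided by EAS size as a crude lower bound. Time and reason of discontinuation are tabulated for the EAS (8.2.1), but they are not crossed with each other or aligned to visit windows. The tables as described do not give the number who stopped for lack of effect before a given visit.

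**The case against.** **A rate that includes stoppers is planned.** A reader might infer that patients who stop are never counted. The documents do not support that. End of treatment is an Appendix 1 visit, so SAP 8.2.4.1 already gives a remission rate with a confidence interval there, and 8.2.4.5 uses it for subgroups. SAP 7 treats completers with no recorded end date as treated to the last observation, so they have this window too. This objection stands, and the point is limited to the fixed visits. The End of treatment rate still has limits. It is not designated primary, it pools very early stops with treatment past Week 60, and it drops stoppers with no complete score in the window. Collection ends at discontinuation, so the two weeks after the last dose may be empty. Protocol 7.3.8 also writes no extension past Week 60, unlike 7.3.3 and 7.3.9.

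**The bias depends on a denominator that the SAP does not state.** If all EAS patients were the divisor, stoppers would already count as non-remitters. That is correct, so the overstatement is conditional. The assessed-patient reading is the natural one, because a patient classed as missing and not imputed has no remission status to enter.

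**Little hangs on one rate.** This is a single-arm survey with no decision rule (SAP 4.2), and every visit is reported. SAP 9 also plans a listing of included patients, whose columns are not given. This lowers the stakes, but it does not tell the reader what the headline rate measures.

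**Conclusion.** The concern holds in a limited form. No primary visit and no per-visit denominator are stated. On the natural reading, the later fixed-visit rates describe patients still treated and scored, and they probably overstate remission in the EAS. No rate counting lack-of-effect stoppers as non-remitters is planned at those visits.

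The size cannot be derived from the documents. It is s(p−m), 13 points in the worked example and 4 to 48 points over the assumed ranges. A reader might infer that the overstatement is certain. It is not, because remission is itself a recorded reason for stopping, and if stoppers are in remission more often than those assessed, the sign reverses.

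The conclusion rests on two assumptions: the divisor is patients assessed in the window, and stoppers are in remission less often than stayers. It is a worthwhile, inexpensive correction to the SAP, not a fault that invalidates the survey.

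**What to change.** In SAP 7 and 8.2.4.1:

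1. Keep the observed-case rate. State its denominator as EAS patients with a complete partial Mayo score in the window, and label it so.
2. Name the fixed visit or visits at which the primary rate is read. The choice is the sponsor's.
3. At those visits only, add a sensitivity analysis among EAS patients whose start date lets them reach the nominal visit day by the data cut-off actually used. Classify each patient once, in this order:
   - a score in the window is used as recorded;
   - no score, and a stop before or within the window for insufficient effectiveness: non-remitter;
   - no score, and a stop for remission: last complete post-baseline partial Mayo status;
   - everyone else without a score, including remission stoppers with no such status: shown both as missing and as non-remitter.
4. Report both results with n, N and the exact 95% CI of SAP 8.1.3, next to the End of treatment rate.

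The cost is a short paragraph of SAP text and some extra programming from stopping dates and reasons already on the CRF. The downside is a figure, probably lower and given as a range, beside the observed-case rate, which is less simple to report.
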